14.2 Database Set-up and Management

The REDCap (Research Electronic Data Capture, Nashville, TN) system will be used as a central resource for data processing and management. REDCap is an open-source software program supported through a consortium led by Vanderbilt University. REDCap is a metadata driven electronic data capture system available for investigators to use for form-based data collection. The system is supported by Emory Library and Information Technologies Services (LITS) and hosted on a LITS virtual machine (VM) environment with nightly backup and full redundancy for high application availability and reliability.

REDCap is a web-based system with the Apache/PHP web server located in the DMZ and the MySQL database backend hosted in a HIPAA- and FDA 21 CFR Part 11-compliant secure data zone. Access to the system requires an Emory University or Emory Healthcare user account with external users (e.g. University of Texas Health Science Center at Houston and NIH) supported using Emory University sponsored accounts. REDCap provides an intuitive interface for data entry with data validation, audit trails for tracking data manipulation and export procedures, automated export procedures for seamless data downloads to common statistical packages, including SAS, and procedures for importing data from external sources. A dedicated database developer will create a study-specific application for data collection.

All data management standards will reflect the goal of reproducible research. To reduce data entry errors and omissions, we will take advantage of REDCap's built-in quality control functions such as branching logic, range and data-type limits, pop-up messages, and prompted data entry. Data integrity is aided by the system's automated logging of all input and edits. Datasets will be clearly identified according to a pre-specified naming system that includes download date. SAS or other programs will be well-commented and be checked for errors by a second programmer or statistician. For quality control and assurance, we will periodically

complete reports on data stored in REDCap. This entails export to our local secure drive, imports as SAS datasets, and production of multiple types of output for data management and reporting. Reports, overall and site-specific, will be provided for data management (e.g., flagging of questionable or missing data and missing forms, variable description, flagging of overdue visits) and for investigators (e.g., screening and enrollment, follow-up tracking, exits).

Microsoft OneDrive will be used as a central repository to store all nasal endoscopy and CT files collected during the course of the study. This HIPPA compliant database will provide access for our central reader while maintaining a backup of study files should additional review be required. All data will be stored with study identification numbers.

14.3 Clinic site data management

Trained study staff will enter data directly to the REDCap application. We will enable auto-validation (via range and data checks) and use skip logic to facilitate data entry and ensure adequate quality.

Data entry personnel will receive standardized training. The study's statistician will examine the distribution of the data for purposes of maintaining integrity of the data. Quality control metrics such as timeliness and completeness of data entry will be reported.

14.4 Randomization

After eligibility is established and consent is obtained, the participants will be randomized on a 1:1 basis to treatment (dupilumab 300 mg every 2 weeks) or placebo. The study biostatistician will prepare a randomization list based on computer-generated random numbers retrieved using a randomization procedure available in statistical packages such as SAS. Block randomization with varying block sizes will be employed to ensure that equal numbers of treatment and placebo participants occur within strata (site) and are balanced with respect to observed and unmeasured baseline factors.

14.5 Statistical Approach

All data will first be assessed by the data management staff, under direction of the lead biostatistician, for missing data and out-of-range values with basic statistical procedures such as univariate statistics (means, standard deviations, ranges, frequencies, proportions, percentiles) and graphs such as histograms, box and whisker plots, scatter plots and Q-Q plots. In addition, plots may be produced of individual and average trajectories of all repeated measures over time according to assigned treatment. All questions of data quality and integrity will be investigated before any statistical modeling, as complete and accurate data are essential for unbiased estimates and confidence intervals.

Baseline and demographic characteristics will be summarized overall for all participants and when applicable, by treatment group. Univariate summary statistics will be provided for continuous variables and frequencies for categorical variables. Graphical methods mentioned above will be used to examine distributions and identify potential influential points. Data transformations for variables may be considered. The balance of baseline measures across the two treatment groups will be compared using appropriate 2-sample tests, including Wilcoxon rank-sum and t-tests, and Fisher's exact and Pearson Chi-square tests. All analyses will be

conducted using SAS version 9.1 for Windows (SAS Institute, Inc., Cary, NC). All analyses will be two-tailed with significance level of 0.05 and conducted using the intention-to-treat principle.

14.6 Primary Analysis

To examine changes in the co-primary outcomes, the modified Lund-Kennedy score and the incidence of oral corticosteroid utilization per participant, a mixed effects longitudinal model will be fit that includes group (dupilumab, placebo) as a between participants factor and time (randomization through post-treatment period) as a categorical within participants factor plus their interaction term. Time is treated as categorical so that we can use the group-time interactions with the time main effect to estimate and test intent-to-treat (ITT) group differences at each time point, with 52 weeks as our primary ITT test. As randomization is stratified by site, site will also be included in the model. This mixed effects model allows incorporation of a random intercept term for each subject, different numbers of measurements (in case a visit is skipped), and the choice of appropriate variance-covariance structure. The mixed model will also permit identification of any significant changes in the post-treatment period from 52 to 64 weeks. This primary mixed model will incorporate all subject's randomized.

The primary objective will be assessed by testing this null hypothesis: treatment with Dupilumab post-surgery is equivalent to treatment with placebo post-surgery at 52-week end of treatment. The additional time point at 64 weeks is included in the model to ensure efficient evaluation of both co-primary outcomes at the EOT and 12 weeks after EOT. Significant changes between weeks 52 and 64 will be examined by linear contrast. We will test the following null hypotheses against two-sided alternatives:

- H₀₁: there is a lack of difference between the changes in mLK from baseline to 52 weeks and from baseline to 64 weeks for the untreated.
- H_{02} : there is a lack of difference between the changes in mLK from baseline to 52 weeks and from baseline to 64 weeks for the treated.
- H_{03} : the treatment effect dissipates between 52 and 64 weeks.

The primary estimand for the primary endpoint is the composite/treatment policy strategy. The intercurrent events will be handled as follows:

- Undergoing sinus surgery for AFRS: data after surgery will be assigned the worst possible score (composite strategy)
- Taking SCS or other rescue medications: data collected after use will be used in the analysis (treatment policy strategy)
- Discontinuing treatment: all data collected after discontinuation will be used in the analysis (treatment policy strategy)

We will examine the treatment effect in the subgroup of patients with unilateral disease by recording patients' time until next sinus surgery. We will investigate differences in this subgroup by examining the Kaplan-Meier curves and utilizing the log rank test of the difference between treated and non-treated. If there is a difference between survival times, we will use the Cox proportional hazard model to account for other relevant covariates such as disease severity.

The Bonferroni correction will be used to account for multiple testing and ensure Type-I error rate remains nominal.

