AFRS

	1	
	BID	Twice a day
	CFR	Code of Federal Regulations
	CRSwNP	Chronic Rhinosinusitis with nasal polyps
	CT	Computed tomography
	EDC	Electronic Data Capture
	FU	Follow-up
	GCP	Good clinical practice
	ICF	Informed consent form
	IMP	Investigational medicinal product
	INCS	Intranasal corticosteroids
	IP	Investigational product
	IPD	IP discontinuation
	IRB	Institutional Review Board
	LMS	Lund-Mackay score
	mLK	Modified Lund Kennedy Endoscopic Score
	SNOT-22	SinoNasal Outcome Test, 22 item
	SoC	Standard of Care
	WOCBP	Women of childbearing potential
Funding	Sanofi	
Source		

Schema

2. Background

Allergic fungal rhinosinusitis (AFRS) is a severe form of eosinophilic nasal polyposis with critically inadequate treatment options for the 10% of chronic rhinosinusitis participants affected by the disease. Occlusive eosinophilic mucus and severe nasal polyposis presents in early adulthood, with an unrelenting course marked by sinus expansion and pressure-induced dehiscence of the surrounding orbit and skull base. Despite appropriate therapies with oral/topical corticosteroids, saline irrigations and comprehensive sinus surgery, nasal polyps aggressively recur, frequently within months of surgery. Medical options beyond topical and systemic steroids are limited. Neither antifungal nor allergen immunotherapy are beneficial. Due to persistent sinonasal inflammation, patients with AFRS receive an average of three corticosteroid bursts per year and revision sinus surgery every 42 months.

Rationale

In addition to the activation of type 2 inflammatory mediators found in other CRSwNP phenotypes, AFRS is uniquely characterized by an exaggerated activation of the adaptive immune response with serum IgE levels often above 1000 kU/L and defined by an upregulation of fungal specific IgE levels [1]. Marked eosinophilic inflammation is found throughout the upper airway, and the degree of mucosal eosinophil infiltration has been repeatedly reported as a potent predictor of poor surgical outcomes. We therefore hypothesize that dupilumab, a human monoclonal antibody that targets the type-2 inflammatory cascade, is a safe and effective treatment for nasal polyps as add-on therapy following endoscopic sinus surgery.

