3.1 Primary Objectives

on initially objectives				
Co-Primary objectives	Endpoint/variable(s)			
	Change from baseline at 52 weeks both within			
	and between treatment and placebo arms			
Determine the efficacy of dupilumab in	Endoscopic modified Lund-Kennedy			
controlling sinonasal inflammation and	(mLK) score			
preventing nasal polyp recurrence after				
complete sinus surgery for AFRS				
 Evaluate the effect of dupilumab on 	• Incidence of oral corticosteroid utilization			
oral corticosteroid utilization following	per participant			
complete sinus surgery for AFRS				

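### The oral-corticosteroid co-primary is tested as a Week 52 visit contrast in the mLK mixed model, and the plan does not say whether that value covers the whole year or only the time since Week 36

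*Combined protocol and SAP*

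**What the plan says.** Section 3.1 lists two co-primary endpoints, the mLK score and "Incidence of oral corticosteroid utilization" per participant, under the column heading "Change from baseline at 52 weeks both within" and between arms.

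Section 14.6 gives both the same analysis: "the modified Lund-Kennedy score and the incidence of oral corticosteroid utilization per participant, a mixed effects longitudinal model will be fit". Time is categorical, and group differences are estimated at each time point, "with 52 weeks as our primary ITT test". The Week 64 time point is kept for "evaluation of both co-primary outcomes at the EOT and 12 weeks after EOT". The model has a random intercept per participant and leaves open "the choice of appropriate variance-covariance structure".

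Section 14.7 mentions a Poisson distribution and a 52-week span, but only for secondary rescue-treatment and adverse-event outcomes. Section 14.1 sizes the trial on mLK alone. Section 4.7.3 records the reason, dose and start and stop dates of every medication.

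**The concern.** The mLK score is read from the endoscopy on the visit day, so a Week 52 contrast is a complete definition. OCS use has no value on a day; it accumulates. Put into the same model, the Week 52 row must hold either use since the Week 36 visit or the total since Week 0. The first reading leaves 36 of the 52 treatment weeks out of the primary test, although section 2 says that "nasal polyps aggressively recur, frequently within months of surgery".

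Two statisticians following section 14.6 could therefore run different primary tests on the same data. Because section 4.7.3 captures dates and reasons, either version could be derived after unblinding. The Bonferroni rule does not protect against a choice between endpoint definitions.

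Other parts of the text also fit mLK and not OCS. Systemic corticosteroid use is listed as an intercurrent event although it is the outcome itself. It is not stated whether the 12-day postoperative taper (section 4.5.3) counts, or whether OCS given for asthma does, with about 25% of participants asthmatic (section 4.1).

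**Working it through.** **The plan's own figure.** Difference 2, SD 3.5, two-sided 0.05, 90% power: the normal approximation gives 65 per group and the t-test gives 66 (power 90.3%). The stated 66 reproduces, but it covers mLK only. The documents give no OCS effect size, dispersion or postoperative rate.

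**Inputs.**
- From the documents: 66 per arm; visits at Weeks 0, 12, 24, 36, 52 and 64; 3 bursts a year (section 2, a general disease figure, not a postoperative rate).
- Assumed: 1 course a year as a lower rate; rate ratio (RR) 0.4-0.7; dispersion k = 0.5 or 1.0; courses spread evenly over time; complete follow-up; alpha 0.025 if Bonferroni splits 0.05 over the two co-primaries (no split is stated).

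**Share of the year.** 52 - 36 = 16 weeks, and 16/52 = 30.8%. At 3 a year a placebo participant has 3.0 expected courses in the year and 3 x 16/52 = 0.92 in the last interval.

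**One case by formula.** For the log rate ratio, SE^2 = [(1/m0 + k) + (1/m1 + k)]/66, with m0 and m1 the expected courses per participant. Take 3 a year, RR 0.5, k = 0.5.
- Full year: (1/3 + 0.5) + (1/1.5 + 0.5) = 2.00; SE = sqrt(2.00/66) = 0.174; 0.693/0.174 - 2.241 = 1.74; power 96%.
- Week 36-52: (1/0.923 + 0.5) + (1/0.462 + 0.5) = 4.25; SE = 0.254; 0.693/0.254 - 2.241 = 0.49; power 69%.
- The variance ratio is 4.25/2.00 = 2.13, so the short window is worth 66/2.13 = 31 participants per arm (38 at k = 1.0; 25-28 at 1 a year).

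**Power by simulation.** Gamma-Poisson counts, 4,000 trials per cell, two-sample t-test, alpha 0.025. Each cell gives k = 0.5 / k = 1.0.

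| Rate, RR | Week 36-52 | Week 0-52 total | Loss (points) |
|---|---|---|---|
| 3/year, 0.4 | 89 / 80% | 99.7 / 97% | 10 / 17 |
| 3/year, 0.5 | 67 / 56% | 95 / 83% | 28 / 27 |
| 3/year, 0.6 | 43 / 33% | 77 / 55% | 33 / 22 |
| 3/year, 0.7 | 22 / 17% | 44 / 28% | 22 / 11 |
| 1/year, 0.4 | 44 / 43% | 91 / 82% | 47 / 40 |
| 1/year, 0.5 | 29 / 25% | 71 / 60% | 42 / 35 |
| 1/year, 0.6 | 17 / 15% | 47 / 34% | 31 / 19 |
| 1/year, 0.7 | 9 / 8% | 24 / 17% | 15 / 9 |

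At alpha 0.05 and RR 0.5 the loss is about 19-23 points at 3 a year and 35-41 at 1 a year.

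**Type I error with a random intercept and constant variance.** This model tests Week 52 with a variance averaged over the five post-baseline rows (Weeks 12 to 64). The count variance is m + k m^2. Take 3 a year, k = 0.5.
- Per-visit values: variance 0.932 for a 12-week interval and 1.349 for the 16-week one; average (4 x 0.932 + 1.349)/5 = 1.015. Ratio 1.349/1.015 = 1.33, square root 1.153. The true level is the two-sided tail beyond 1.96/1.153 = 1.70, which is 0.089.
- Cumulative values: variances 0.93, 2.34, 4.23, 7.50 and 10.51; average 5.10. Ratio 7.50/5.10 = 1.47, square root 1.212. The tail beyond 1.96/1.212 = 1.62 is 0.106.

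Across the four rate and dispersion settings, simulation gives about 0.08-0.09 per-visit and 0.10-0.11 cumulative at nominal 0.05. Unstructured covariance with cumulative counts gave 0.046-0.055.

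**The case against.** The strongest reply is that the intent can be read. Section 3.2 separates incidence per subject from prevalence per treatment cohort, section 5.2 speaks of the number of rescue medications per subject, and section 14.10 expects more frequent rescue use on placebo. Together these point to a per-participant count over the year. That stands, and it makes a simple any-use endpoint an unlikely reading. It does not settle the test: section 5.2 covers all rescue drugs, section 14.10 is an expectation, and the 52-week and Poisson wording of section 14.7 is confined to secondary outcomes. Section 14.6 specifies a visit contrast.

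Three further replies also stand:
- The change-from-baseline heading is generic. In section 3.2 it also covers prevalence of revision surgery, where it cannot apply, so it should not be read as an OCS definition.
- The worst-score rule speaks of a score and of one primary endpoint, so it most naturally means mLK. One clarifying sentence is enough.
- Negative binomial regression is a choice. It gains only 0-4 points over a t-test on the 52-week total, and its Wald test ran slightly liberal (0.028-0.031 at nominal 0.025).

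A reader might infer that counting the taper for everyone is harmless because it only dilutes the rate ratio. That fails for a negative binomial test: at 1 a year, RR 0.5 and alpha 0.025, adding one course to everyone cuts simulated power from about 62-73% to about 44-45%.

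**Conclusion.** The concern holds. Section 14.6 applies a visit-state model to an outcome that accumulates, and no section fixes the counting window of a co-primary endpoint. This can be seen from the text without any power assumption.

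The size is conditional. The loss from testing Week 36-52 rather than the year is about 10-33 points at 3 courses a year and 9-47 at 1 a year, over RR 0.4-0.7 at alpha 0.025. The rate ratio, dispersion, even timing, alpha split and lower rate are all assumed.

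Two stronger readings are not supported. A reader might infer that the trial will in fact test only the last 16 weeks and lose this power; the documents do not say so, and a full-year count is the likelier intent. A reader might also infer that type I error will be inflated; that needs constant variance, and section 14.6 leaves the covariance open. The plan's 66 per group is not in error. Stratification factors, the allocation of alpha under Bonferroni, and the absence of an OCS power calculation are separate matters.

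**What to change.** In section 14.6, take OCS out of the mLK visit model and state:
- **Endpoint.** The number of OCS courses started from Week 0 to Week 52, derived from the dates and reasons recorded under section 4.7.3.
- **Indication.** Whether only courses for chronic rhinosinusitis count, or all courses, including those for asthma.
- **Taper and merging.** The planned postoperative taper is excluded by its recorded reason. The rule for merging adjacent records applies only to non-taper records. With surgery near Day -7, a 12-day taper ends near Day 5, and a merging rule applied to all records could absorb a new course begun soon after.
- **Comparison.** A rate ratio from a count model that allows overdispersion (negative binomial, or Poisson with robust variance), with log follow-up time as offset and adjustment for the randomization strata.
- **Incomplete follow-up.** The offset handles it for this outcome in place of the section 14.8 imputation.
- **Revision surgery.** The worst-score rule applies to mLK only; OCS courses after revision surgery are counted as observed.
- **Week 52-64.** Analysed separately.

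The cost is one amendment before unblinding, with the usual IRB and DSMB review, and one more model to program. No new data are needed and clinical management does not change. The fix does not guarantee power: at RR 0.6 and 3 a year, a full-year negative binomial test still has only 59-79% at alpha 0.025.

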Project Title	S-I A randomized, 52-week treatment double-blind, placebo-controlled efficacy and safety study of dupilumab 300 mg every other week after endoscopic sinus surgery in participants with allergic fungal rhinosinusitis (AFRS) on a background therapy with intranasal corticosteroid spray Short: Add-on Dupilumab for AFRS as Postoperative Therapy (ADAPT)				
Project Design	Multicenter, randomized, double-blind, placebo-controlled study comparing the efficacy of dupilumab to placebo in allergic fungal rhinosinusitis (AFRS) participants after sinus surgery on a background treatment with intranasal corticosteroid spray				
	Study periods: The clinical trial consists of 4 periods: 1. Run-in period (2 weeks + 4 weeks): All participants will enter a run-in period of 2-6 weeks receiving saline irrigations and INCS spray daily. All oral steroids and antibiotics as well as corticosteroid rinses will be stopped. 2. Surgery period (7 days + 4 weeks): Patients will undergo surgery as scheduled. Sinonasal mucus, peripheral blood and ethmoid tissue will be collected from all participants at the time of surgery. 3. Randomized treatment (52 weeks ± 7 days): Patients will be randomized to one of the following treatments: • Arm A: dupilumab 300 mg subcutaneous (SC) q2w until Week 52 • Arm B: placebo given SC q2w until Week 52 4. Posttreatment period (12 weeks ± 3 days): After completing 52 weeks of treatment with IMP (or following early discontinuation of IMP or discontinuation from the study), participants will be instructed to • Return to the study site for the last scheduled visits for physical examination, nasal endoscopy, NPS, PROs (SNOT-22 and ACQ), FEV1 measurement in those with asthma and safety. • Continue on stable dose of INCS spray during the posttreatment period.				
	Report any adverse event (AE).				
Co-Primary Objectives	 a) Determine the efficacy of dupilumab in controlling sinonasal inflammation and preventing nasal polyp recurrence after complete sinus surgery for AFRS, as measured by change in the mLK score b) Evaluate the effect of dupilumab on oral corticosteroid utilization following complete sinus surgery for AFRS 				
Secondary	To evaluate the effect of dupilumab on:				
Objectives	Prevention of revision surgery for AFRS				
Objectives	 				
	 Secondary objective measures of sinonasal inflammation following sinus surgery using the NPS and LMS 				
	 Lower airway dysfunction following sinus surgery in the subgroup of 				

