5.2.1 Objective measures of disease

Modified Lund-Kennedy Endoscopic Score:

Modified Lund-Kennedy score (mLK) is a validated measure of sinonasal inflammation, as evaluated by means of nasal endoscopy. The composite score ranges from 0 to 12, with increasing score representing worsening inflammation among three separate findings (Nasal polyps, Discharge, Edema). Each finding is rated from 0 (absent) to 2 (severe). $A \ge 2$ -point increase from baseline total postoperative score represents clinically significant worsening of sinonasal inflammation[5]. The treating physician will complete the nasal endoscopy per SoC,

with automated recording on local storage drives. Following completion of the patient encounter, study personnel will transfer this recording to the study database for central review and scoring. A blinded reader will review all nasal endoscopies to determine the mLK score.

Lund-MacKay Radiologic Score:

The change in radiographic opacification between baseline and EOT will be analyzed by the Lund- MacKay radiologic score (LM) [6]. The LM Radiologic scoring system assigns a value of 0, 1, or 2 to each of the following sinuses: maxillary, anterior ethmoid, posterior ethmoid, frontal, and sphenoid. Score assignments are 0 if the sinus is totally patent, 1 if the sinus is partially opacified, and 2 if the sinus is completely opacified. The osteomeatal complex is scored either 0 if not occluded or 2 if occluded. The maximum score for each side is thus 12, with a total score determined out of 24. Baseline LM scores will be assessed from baseline preoperative CT scan. Preoperative and EOT CT scans will be transferred to the study database by trained personnel, where the blinded reader may determine the associated LM score.

Endoscopic Nasal Polyp Score:

Endoscopic nasal polyp score is determined by the treating Investigator. Unlike prior study of dupilumab in nasal polyps, [7] we will separately record the Nasal Polyp Score for each side, with a maximum unilateral score of 4. This is appropriate for monitoring efficacy in AFRS, as a subgroup of participants may present with unilateral disease. This will be considered in statistical analysis and reporting of results (see Section 14.6- Primary Analysis).

Table 5: Endoscopic Nasal Polyp Score

Polyp Score	Polyp Size
0	No polyps
1	Small polyps in the middle meatus not reaching below the inferior border of
	the middle turbinate
2	Polyps reaching below the lower border of the middle turbinate

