14.1 Sample Size and Power analysis

A sample size of 66 participants per group achieves 90% power to detect a mean difference of 2 points on the modified Lund-Kennedy Endoscopic score at 52 weeks with a standard deviation of 3.5 and significance level of 0.05 using a two-tailed test. The clinically meaningful mean difference of 2 points and the standard deviation are based on previous study of mLK in a heterogeneous population with nasal polyps [5].

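### Section 14.6 does not write out the Week-52 mLK contrast, and it enters Week 0 mLK only as a free outcome level, so score difference and change from baseline remain two different tests

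*Combined protocol and SAP*

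**What the plan says.** Section 14.6 fits a mixed model with group, categorical time running from randomisation to the post-treatment period, their interaction, site and a random intercept. It will "use the group-time interactions with the time main effect to estimate and test intent-to-treat (ITT) group differences at each time point" and makes Week 52 the primary test. The null is that "treatment with Dupilumab post-surgery is equivalent to treatment with placebo post-surgery at 52-week end of treatment". The section also leaves open "the choice of appropriate variance-covariance structure".

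Other places describe the mLK comparison on one scale or the other:

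- **Score.** Section 14.1 sizes the trial to "detect a mean difference of 2 points on the modified Lund-Kennedy Endoscopic score at 52 weeks", with an SD of 3.5.
- **Change.** Section 3.1 heads the endpoint column "Change from baseline at 52 weeks both within" and between arms. Co-primary objective (a) in the Study Summary is "as measured by change in the mLK score". Section 14.6 itself opens by saying that it examines changes in the co-primary outcomes.
- **Meaning of 2 points.** Section 5.2.1 cites the same source as 14.1 and says of a rise of at least 2 points: "increase from baseline total postoperative score represents clinically significant worsening of sinonasal inflammation".

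Table 1 has mLK scored at Weeks 0, 12, 24, 36, 52 and 64, so the mLK baseline is Week 0, after surgery. No section makes Week 0 mLK a covariate or sets its mean equal across arms.

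**The concern.** In a group-by-time model with Week 0 as an unconstrained outcome level, the difference in Week-52 scores and the difference in change from Week 0 are separate contrasts with separate standard errors. They can give different answers in the same trial. The plan leans to one in some places and describes the other elsewhere, and does not write the deciding contrast down.

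Two things are at stake. One is an open choice in a co-primary test, which costs type I error if it is settled after the data are seen. The other is precision: Week 0 mLK will be collected, but in this form it does not sharpen the Week-52 comparison.

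**Working it through.** **1. Which coefficients give which contrast.** Write E[Y] = b0 + b1·group + b2t·time + b3t·group×time, with Week 0 as reference.

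- Difference in Week-52 scores: b1 + b3(52).
- Difference in change from Week 0: b3(52) alone.
- Interaction plus time main effect, the terms 14.6 names: b2(52) + b3(52). This is the change within the dupilumab arm, not a between-arm difference.

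A fit to simulated data confirmed all three. With an effect of 2 points, both between-arm contrasts averaged 2.00 in size, so both are unbiased under randomisation.

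**2. The plan's own figure.** Inputs from 14.1: 66 per arm, difference 2, SD 3.5, two-sided 0.05. SE = 3.5 × √(2/66) = 0.609, and 2/0.609 = 3.28. The noncentral t gives 90.3% power, and 66 is the smallest number per arm that reaches 90%. The figure reproduces.

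**3. Power of the alternatives.** Two quantities are not in the documents and are assumed over a range: r, the correlation between Week 0 and Week 52, and k, the Week 0 SD divided by the Week 52 SD. Week 0 follows surgery and the prednisone taper in Section 4.5.3, so k below 1 is plausible. Data are taken as complete and 3.5 as the SD of the Week-52 score.

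- SD of change = 3.5 × √(1 + k² − 2rk). At r = 0.3 this is 3.5 × √1.4 = 4.14 for k = 1, and 3.5 × √0.95 = 3.41 for k = 1/2.
- Baseline-adjusted SD = 3.5 × √(1 − r²). At r = 0.3 this is 3.5 × √0.91 = 3.34, whatever k is.

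| r | Score | Change, k=1 | Change, k=1/2 | Change, k=1/3 | Adjusted |
|---|---|---|---|---|---|
| 0.2 | 90.3% | 73.1% | 88.9% | 90.9% | 91.4% |
| 0.3 | 90.3% | 78.6% | 91.7% | 92.7% | 92.7% |
| 0.5 | 90.3% | 90.3% | 96.4% | 95.9% | 96.4% |
| 0.7 | 90.3% | 98.8% | 99.3% | 98.2% | 99.5% |

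With Week 0 mLK as a covariate, the analyses of score and of change give the same treatment estimate and SE (checked numerically).

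**4. Cost of leaving the choice open** (40,000 simulated trials per setting, r from 0.2 to 0.7).

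| | k=1 | k=1/2 | k=1/3 |
|---|---|---|---|
| Tests disagree, true effect 2 points | 10-23% | 6-9% | 5-8% |
| Either test rejects, no effect | about 9% | 7-8% | 6-7% |

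**5. If 3.5 is the SD of change instead.** The change test then has 90.3% power throughout. The score SD is 3.5/√(1 + k² − 2rk), and the score test has 98.5/97.1/90.3/71.4% at r = 0.2/0.3/0.5/0.7 with k = 1, or 91.6/88.8/80.6/67.6% with k = 1/2.

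**6. Covariance.** With a random intercept alone (six visits, complete data, r = 0.3 to 0.7), the Week-52 score test has a type I error of about 5% if the SDs are equal. If the SD doubles steadily from Week 0 to Week 52, it is about 11.5% when the SD is flat afterwards and about 10.5% when it keeps widening.

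**The case against.** The best defence is that the plan already leans one way. Section 14.6 promises between-arm differences visit by visit with Week 52 primary, and 14.1 powers a score difference at 52 weeks. The change wording in 3.1 is a column header that also covers incidence of corticosteroid use. The same header in 3.2 covers revision surgery and survival curves, where change from baseline has no clear meaning. This stands in part: it would be wrong to say that nothing indicates which test decides. But the Study Summary objective and the opening of 14.6 also speak of change, and the coefficients 14.6 names yield neither between-arm contrast.

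The largest figures also need equal SDs at Week 0 and Week 52. With a narrower Week 0 spread the score and change tests nearly coincide. That stands, and the smaller figures are probably nearer the truth.

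A reader might infer more than the documents support:

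- **That Week 0 mLK is ignored.** The time factor starts at randomisation, so Week 0 is an outcome level. What is missing is a covariate or a common mean, the forms that would make the two contrasts coincide.
- **That the primary test is within one arm.** The same sentence speaks of differences between groups, so naming the time main effect is loose wording.
- **That the 14.6 null fixes the score scale.** It names no scale.
- **That the planned model inflates the type I error to 10-12%.** That needs a random intercept alone and a strongly widening SD, and 14.6 allows another covariance structure.

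**Conclusion.** The point holds as a gap in specification with a cost in precision. It is not a bias and not an error in the sample size. The plan leans to the Week-52 score difference, describes change from baseline elsewhere, and does not write out the contrast.

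Taking 3.5 as the score SD, baseline adjustment lifts power from 90% to 91/93/96/99.5% at r = 0.2/0.3/0.5/0.7. The gain is therefore about 1 point at low correlation and 6 points at r = 0.5. Using the change test instead could cost up to 17 points (90% against 73%, at r = 0.2 with equal SDs) or almost nothing (90% against 89%, if the Week 0 SD is half). The type I error of about 6-9% arises only if the test is picked after the data are seen. A reader might infer that this is intended; nothing in the documents suggests so.

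All of this rests on assumed values of r and k, complete data and the 0.05 level of 14.1. Section 14.6 also says "The Bonferroni correction will be used to account for multiple testing" without giving the number of tests. If the level were 0.025, an assumption, the score test would have 84% and the adjusted test 86/88/94/99%. The text should be settled before unblinding.

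**What to change.** 1. In Section 14.6, state for mLK: *The primary mLK test is the between-arm difference at Week 52 from a mixed model with Week 0 and all later visits as outcomes, visit, group-by-visit terms with the Week 0 mean constrained equal across arms, the randomisation strata, and an unstructured covariance.*
2. Align Section 3.1, the Study Summary objective and Section 14.1 with this contrast, and say in 14.1 whether 3.5 is the SD of the score or of the change.

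With a common Week 0 mean, the difference in Week-52 scores and the difference in change become the same contrast. Because Week 0 stays an outcome, randomised participants without a later mLK remain in the model, as 14.6 intends, and within-arm change from baseline can still be estimated as 3.1 asks. The constraint relies on Week 0 mLK being unaffected by treatment. The first dose is given at the same visit, so it is worth stating that the endoscopy is recorded before the injection.

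The cost is a few more covariance parameters: six visits need 6 × 7/2 = 21, which is feasible with 132 participants. No new data or participants are needed. The corticosteroid contrast, the wording of the strata, H03 and confounder selection are separate matters and not part of this point.
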